9.3 Clinical Laboratory Data

Clinical laboratory tests include serum chemistry analysis, hematology analysis, urinalyses and other lab analysis. The potentially clinically relevant laboratory test abnormalities are listed by subject and by test for the safety samples. Criteria for identifying laboratory values of the potential clinical relevance are provided in [Appendix 1](#). Subjects with AST or ALT > 3 times upper limit of normal (ULN) value and total

bilirubin > 2 times ULN values if pre-treatment value is \leq ULN value, or with AST or ALT > 3 times pre-treatment value and total bilirubin > 2 times pre-treatment value if pre-treatment value is > ULN value, are listed by phase. The incidences of potentially clinically relevant laboratory tests abnormalities based on the observation from the scheduled and the unscheduled post-baseline visits will be tabulated for the safety samples. Descriptive statistics for the clinical laboratory measurements and changes from baseline at each scheduled trial week and last visit will be presented for the safety samples.

If laboratory tests assessments are repeated for the same visit, the last repeated values are used for summary tables. This is accomplished by sorting patient data by visit date and visit time (if applicable) within the same visit identification. If the lab data are recorded as ranges (i.e., including < or > limit of quantification), these data are not included in the calculations for changes from baseline but included in the calculations for incidences.

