Any value outside the normal range will be flagged for the attention of the investigator who must indicate whether or not a flagged value is of clinical significance. If one or more values are questionable, the test(s) may be repeated. If the result of any test (or repeat test, if done) is indicated as clinically significant in the samples taken during the screening period, the subject will NOT be enrolled into the trial without the permission of the medical monitor. In addition, follow-up unscheduled laboratory tests should be performed for clinically significant abnormalities. Unscheduled laboratory tests may be repeated at any time at the discretion of the investigator for appropriate medical care.

Subjects will be excluded from the trial if they have any other abnormal laboratory test result at screening that, in the investigator's judgment, is medically significant in that it would impact the safety of the subject or the interpretation of the trial results. The following laboratory test results are exclusionary:

- 1) Platelets $\leq 75,000/\text{mm}^3$
- 2) Hemoglobin $\leq 9 \text{ g/dL}$
- 3) Neutrophils, absolute $\leq 1000/\text{mm}^3$
- 4) Aspartate aminotransferase (AST) $> 3 \times$ upper limit of normal (ULN) as defined by the central laboratory
- 5) Alanine aminotransferase (ALT) $> 3 \times$ ULN as defined by the central laboratory
- 6) Creatinine $\geq 2 \text{ mg/dL}$

Protocol 31-14-204

[Appendix 2](#) is included to assist investigators in their assessments of results that may be of potential clinical relevance, depending on the subject's medical history and clinical presentation.

Table 3.7.3.2-1 Clinical Laboratory Assessments	
Hematology: Hematocrit Hemoglobin Platelet count Red blood cell count White blood cell count with differential	Serum Chemistry: Alkaline phosphatase ALT AST Total bilirubin Blood urea nitrogen Calcium Chloride Cholesterol (total, low-density lipoprotein, and high-density lipoprotein) Creatinine Creatinine phosphokinase Gamma glutamyl transferase Glucose Glycosylated hemoglobin Lactate dehydrogenase Phosphorus, inorganic Potassium Total protein Sodium Triglycerides Uric acid
Urinalysis: Blood Glucose Ketones Microscopic exam (performed only if any part of the urinalysis is not negative) pH Protein Specific gravity	Additional Tests: Prolactin ^b Serum pregnancy, for confirmation of positive urine tests TSH ^a Urine drug (including alcohol) screen Urine pregnancy (FOCBP)

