5.1 Definitions

An AE is defined as any untoward medical occurrence in a patient or clinical trial subject administered a medicinal product and which does not necessarily have a causal

Protocol 31-14-204

relationship with this treatment. AEs would not include information recorded as medical history at screening for preplanned procedures for which the underlying condition was known and no worsening occurred. An adverse reaction is any untoward and unintended response to an IMP-related to any dose administered.

A suspected adverse reaction is any AE for which there is a reasonable possibility that the IMP caused the AE. For the purpose of Investigational New Drug (IND) safety reporting, "reasonable possibility" means there is evidence to suggest a causal relationship between the IMP and the AE. Suspected adverse reaction implies a lesser degree of certainty about causality.

An SAE includes any event that results in any of the following outcomes:

- Death
- Life-threatening; ie, the subject was, in the opinion of the investigator, at immediate risk of death from the event as it occurred. It does not include an event that, had it occurred in a more severe form, might have caused death.
- Persistent or significant incapacity/disability or substantial disruption of the ability to conduct normal life functions.
- Requires in-patient hospitalization or prolongs hospitalization.
 - Hospitalization itself should not be reported as an SAE; whenever possible the reason for the hospitalization should be reported.
 - Hospitalizations or prolonged hospitalizations for social admissions (ie, those required for reasons of convenience or other non-medical need) are not considered SAEs.
- Congenital anomaly/birth defect.
- Other medically significant events that, based upon appropriate medical judgment, may jeopardize the subject and may require medical or surgical intervention to prevent one of the outcomes listed above; eg, allergic bronchospasm requiring intensive treatment in an emergency room or home, blood dyscrasias or convulsions that do not result in hospitalization, or the development of drug dependency or drug abuse.

Nonserious AEs are all AEs that do not meet the criteria for a "serious" AE.

Immediately Reportable Event (IRE):

- Any SAE.
- Any AE related to occupational exposure.
- Potential serious hepatotoxicity (see [Section 5.4](#)).

Protocol 31-14-204

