5.4 Potential Serious Hepatotoxicity

For a subject who experiences an elevation in AST or ALT that is ≥ 3 times the ULN, a total bilirubin level should also be evaluated. If the total bilirubin is ≥ 2 times the ULN, complete an IRE form with all values listed and also report as an AE on the eCRF.

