- CT-8.6.2 Incidence of Treatment-Emergent Adverse Events Resulting in Discontinuation from Trial by System Organ Class, MedDRA Preferred Term and Severity (Randomized Safety Sample)
- CT-9.1 Listing of Deaths (Safety Sample)
- CT-9.2 Listing of Serious Adverse Events (Safety Sample)
- CT-9.3 Listing of Discontinuations of Study Medication Due to Adverse Events(Safety Sample)
- CT-10.1.1 Laboratory Test Results for Serum Chemistry - Mean Change from Baseline (Randomized Safety Sample)
- CT-10.1.2 Laboratory Test Results for Hematology - Mean Change from Baseline (Randomized Safety Sample)
- CT-10.1.3 Laboratory Test Results for Urinalysis - Mean Change from Baseline (Randomized Safety Sample)
- CT-10.1.4 Laboratory Test Results for Other Clinical Laboratory Tests - Mean Change from Baseline (Randomized Safety Sample)
- CT-10.2 Incidence of Laboratory Values of Potential Clinical Relevance (Randomized Safety Sample)
- CT-10.3.1 Listing of Laboratory Values of Potentially Clinical Relevance by Subject(Safety Sample)
- CT-10.3.2 Listing of Laboratory Values of Potentially Clinical Relevance by Type (Safety Sample)
- CT-10.3.3 Criteria for Laboratory Values of Potentially Clinical Relevance
- CT-10.4 Listing of Potentially Liver Injury Related Laboratory Test Abnormalities by Subject (Safety Sample)
- CT-11.1.1 Vital Sign Parameters - Mean Change from Baseline (Randomized Safety Sample)
- CT-11.1.2 Mean Change from Baseline in Weight, Height, BMI and Waist Circumference (Randomized Safety Sample)
- CT-11.2 Incidence of Vital Signs of Potential Clinical Relevance (Randomized Safety Sample)
- CT-11.3.1 Listing of Vital Signs of Potentially Clinical Relevance by Subject(Safety Sample)
- CT-11.3.2 Criteria for Potentially Clinically Relevant Vital Sign Abnormalities
- CT-12.1 ECG Parameters - Mean Change from Baseline (Randomized Safety Sample)
- CT-12.2 Incidence of ECG Measurements of Potential Clinical Relevance (Randomized Safety Sample)
- CT-12.3.1 Listing of ECG Measurements of Potentially Clinical Relevance (Safety Sample)
- CT-12.3.2 Criteria for ECG Measurements of Potentially Clinical Relevance
- CT-13.1.1 Simpson-Angus Scale Total Score - Mean Change from Baseline by Week - OC (Open-Label Safety Sample)
- CT-13.1.2 Barnes Akathisia Rating Scale Global Score - Mean Change from Baseline by Week - OC (Open-Label Safety Sample)
- CT-13.1.3 AIMS Movement Rating Score - Mean Change from Baseline by Week - OC (Open-Label Safety Sample)

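### The SAP's liver-injury listing (CT-10.4) uses a different combined criterion from Protocol 5.4, so a subject who meets the protocol's immediately reportable rule can be absent from it (minor)

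*SAP*

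**What the plan says.** **Protocol 5.4** sets a reporting trigger in fixed multiples of ULN. The transaminase part reads "For a subject who experiences an elevation in AST or ALT that is ≥ 3 times the ULN"; bilirubin is then evaluated, and "If the total bilirubin is ≥ 2 times the ULN, complete an IRE form with all values listed". The case must also be reported as an adverse event. Neither part mentions the baseline value. Protocol 5.1 counts potential serious hepatotoxicity as an immediately reportable event, separately from SAEs.

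**SAP 9.3** describes a combined listing with two branches. For a pre-treatment value at or below ULN it covers "Subjects with AST or ALT > 3 times upper limit of normal (ULN) value and total" bilirubin above 2 x ULN. For a pre-treatment value above ULN it covers those "with AST or ALT > 3 times pre-treatment value and total bilirubin > 2 times pre-treatment value". The word joining the branches separates two baseline situations; it does not offer an elevated-baseline subject a second way in. The matching output in SAP Appendix 4 is CT-10.4.

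**Eligibility** (Protocol 3.4.3, criterion 20, and 3.7.3.2) excludes AST or ALT only above 3 x ULN and sets no numeric limit for bilirubin. Other abnormal screening results exclude a subject if the investigator judges them medically significant.

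**SAP Appendix 1** flags single tests without reference to baseline for these analytes: AST or ALT at least 3 x ULN, and total bilirubin at least 2.0 mg/dL. These flags feed CT-10.3.1 (by subject) and CT-10.3.2 (by type).

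**The concern.** CT-10.4 is the only output in the available text of Appendix 4 defined by transaminase and bilirubin together. A reader who finds it empty would naturally conclude that no subject reached the combined level that the protocol treats as immediately reportable. With the SAP's rule that conclusion could be wrong, because the threshold for listing rises with the baseline while the reporting trigger does not. Safety and tolerability is the trial's secondary objective. With efficacy reduced to descriptive summaries after early termination, the safety listings carry much of the report's content.

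**Working it through.** There is no stated figure to reproduce. The check puts both rules in multiples of ULN and runs the same subjects through each.

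**Rules.** Let A and B be the on-treatment AST/ALT and bilirubin, and A0 and B0 the pre-treatment values.

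- Protocol 5.4: A >= 3 and B >= 2.
- SAP 9.3, pre-treatment value <= 1: A > 3 and B > 2.
- SAP 9.3, pre-treatment value > 1: A > 3 x A0 and B > 2 x B0.

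**Transaminase level needed when A0 is elevated** (3 x A0, against a constant 3 in the protocol):

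| A0 (x ULN) | SAP needs more than (x ULN) |
|---|---|
| 1.1 | 3.3 |
| 1.5 | 4.5 |
| 2.0 | 6.0 |
| 2.5 | 7.5 |
| 3.0 (highest eligible) | 9.0 |

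**Which value triggers the switch?** SAP 9.3 does not say. Four readings are possible: (1) each analyte switches on its own baseline; (2) both switch on the AST/ALT baseline; (3) both switch if either baseline is elevated; (4) both switch on the bilirubin baseline, because the condition stands next to bilirubin in the sentence. The first three share the natural reading that an elevated AST/ALT baseline raises the AST/ALT threshold. All subject values below are assumed for illustration, in x ULN.

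| Case | ALT | Bilirubin | Meets Protocol 5.4 | Listed: (1) | (2) | (3) | (4) |
|---|---|---|---|---|---|---|---|
| A | 2.0 to 5.0 | 0.5 to 2.5 | yes | no | no | no | yes |
| B | 3.0 to 8.9 | 0.5 to 2.5 | yes | no | no | no | yes |
| C | 1.1 to 3.2 | 0.5 to 2.5 | yes | no | no | no | yes |
| D | 0.8 to 5.0 | 1.5 to 2.9 | yes | no | yes | no | no |
| E | 0.8 to 3.0 | 0.5 to 2.0 | yes | no | no | no | no |
| F | 2.0 to 5.9 | 1.5 to 2.9 | yes | no | no | no | no |
| G | 2.0 to 6.5 | 0.5 to 1.2 | no | no | yes | yes | no |

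Case A fails under readings 1 to 3 because 5.0 is not above 3 x 2.0 = 6.0. Under reading 4 its bilirubin baseline is normal, so 5.0 > 3 and 2.5 > 2 put it on the listing. Case D turns on whether 2.9 must exceed 2 x 1.5 = 3.0 or only 2. Case E is missed solely because the SAP uses > where the protocol uses >=. Case F is missed under every reading: either 5.9 is not above 6.0, or 2.9 is not above 3.0, or both. Case G shows the reverse: 6.5 > 6.0 and 1.2 > 2 x 0.5 = 1.0, so two readings list a subject who does not meet Protocol 5.4.

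**Which phase?** The listing is by phase, but the pre-treatment value is not tied to one. SAP 5.2 takes the double-blind baseline from the last open-label visit, when the subject is on aripiprazole. If that value is used, a subject whose ALT had risen to 2.5 x ULN during open-label treatment would need > 7.5 x ULN in the double-blind phase to be listed.

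**What the other output still shows.** Appendix 1 flags AST/ALT at 3 x ULN regardless of baseline, so the transaminase values in cases A to F all appear in CT-10.3.1. The bilirubin criterion is absolute: a value of exactly 2 x ULN reaches 2.0 mg/dL only if ULN is at least 2.0/2 = 1.0 mg/dL. The documents give no ULN. Over an assumed range of 0.8 to 1.3 mg/dL, 2 x ULN runs from 1.6 to 2.6 mg/dL, so some qualifying bilirubin values would go unflagged at the low end. In case A, 2.5 x 0.8 = 2.0 mg/dL, so its bilirubin is flagged across that whole range.

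**The case against.** The strongest reply is that Protocol 5.4 and CT-10.4 have different jobs. Section 5.4 tells investigators what to report. The protocol's plan for laboratory analysis (7.6.2) asks only for incidences of potentially relevant values and changes from baseline, and contains no combined liver listing. CT-10.4 is an SAP addition, and nothing in the SAP says that it implements 5.4. Scaling to an elevated baseline is also a reasonable way to separate on-treatment change from a stable pre-existing elevation. All of this stands. A reader might infer that the SAP silently abandons a planned analysis; the documents do not support that.

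Two other stronger inferences also fail.

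- *The case vanishes from the trial's output.* It does not. Protocol 5.4 requires an adverse event report, which should reach AE-1.1 or AE-1.2. CT-10.3.1 is organised by subject, so both flags can appear together, and LAB-1 covers serum chemistry.
- *Elevated baselines are to be expected.* The documents show only that they are permitted. Clinically significant screening results require a repeat and investigator clearance (3.7.1.1) or the medical monitor's permission (3.7.3.2), and medically significant abnormalities exclude. A baseline of 3 x ULN is the extreme, since that subject already meets the protocol's transaminase threshold before any dose.

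The size of the gap also depends on an ambiguous sentence: under reading 4, cases A to C would be listed. What survives is narrower. The two criteria differ, the difference is unexplained, and under every reading at least some subjects who meet Protocol 5.4 are not in CT-10.4.

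**Conclusion.** The point holds as a minor inconsistency in safety reporting. On the natural reading, a baseline ALT of 1.5 to 3 x ULN raises the listing threshold to > 4.5 to > 9 x ULN, against a fixed 3 x ULN in Protocol 5.4. The strict inequality also drops values exactly at the thresholds, even with normal baselines. The loss is confined to the formal joint display. The transaminase value should still be visible in CT-10.3.1 and the event in the adverse event listings; the bilirubin value is usually visible too, subject to the laboratory's ULN.

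Few subjects are likely to be affected: each needs a baseline above ULN that was not judged medically significant (or an exact-threshold value), and must then reach both protocol thresholds on treatment. The documents give no rate for any of these. No estimate or test changes. The conclusion rests on the text of the two rules; the subject values and the bilirubin ULN range are assumptions used for illustration.

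**What to change.** Reconcile SAP 9.3 with Protocol 5.4 for reporting purposes:

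1. Have CT-10.4 also list every subject with post-baseline AST or ALT >= 3 x ULN and total bilirubin >= 2 x ULN, regardless of baseline.
2. Keep the baseline-relative rule as a flag in the same listing, so that change from an elevated baseline stays visible.
3. State which analyte's pre-treatment value triggers the switch, and whether it is the value before the first open-label dose or the phase baseline in SAP 5.2.

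The cost is a wording change in the SAP, one added condition and a flag in the listing program. No new data are needed. The downside is that a few subjects with stable elevated baselines may also be listed; the flag lets a reader tell them apart. The change concerns what the listing displays and leaves the protocol's reporting rule as it is.

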9.	The subject represents a significant risk of committing suicide based on history (suicide attempt in past 1 year), routine psychiatric status examination, investigator's judgment, or who have an answer of "yes" on any question other than 1-3 (current or over the last 30 days) on the baseline/screening version of the C-SSRS.
10.	The subject has a body weight < 16 kg.
11.	Subjects who have taken neuroleptic or antiparkinson drugs within 14 days prior to baseline.
12.	Subjects requiring CBT for TD during the trial period. CBT for other nonexclusionary disorders must remain consistent throughout the trial.
13.	The subject has met DSM-5 criteria for any significant psychoactive substance use disorder within the past 3 months.
14.	A positive drug screen for cocaine, alcohol, or other drugs of abuse (excluding caffeine, nicotine, or prescribed psychostimulants for ADHD). Investigators can choose to repeat a positive drug screen one time during screening period after concurrence from the medical monitor. A second positive test for any drug of abuse would be exclusionary.
15.	Subject requiring medication not allowed per protocol.
16.	Use of any CYP2D6 and CYP3A4 inhibitors or CYP3A4 inducers within 14 days prior to baseline and for the duration of the trial.
17.	Other nutritional or dietary supplements and nonprescription herbal preparations for TD (eg, cannabinoids, N-acetylcysteine, omega-3 fatty acids, kava extracts, GABA supplements) within 7 days prior to baseline and for the duration of the trial, unless approved in advance by the medical monitor.
18.	The inability to swallow tablets or tolerate oral medication.
19.	Subject has participated in a clinical trial involving either study medication or interventional (non-medication) treatment for TD within the last 60 days.
20.	The following laboratory test results, vital signs and ECG results are exclusionary: 
 a) Platelets $\leq 75,000/\text{mm}^3$ b) Hemoglobin ≤ 9 g/dL c) Neutrophils, absolute $\leq 1000/\text{mm}^3$ d) AST $> 3 \times \text{ULN}$ as defined by the central laboratory e) ALT $> 3 \times \text{ULN}$ as defined by the central laboratory f) Creatinine ≥ 2 mg/dL g) Diastolic blood pressure > 105 mmHg h) QTc ≥ 450 msec (males) or ≥ 470 msec (females) using the QTcF correction.

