7.6.2 Clinical Laboratory Data

The incidence of potentially clinically relevant values from clinical laboratory tests will be provided for the open-label stabilization phase and by treatment group for the randomized withdrawal phase with the safety samples appropriate to each phase. In addition, change from baseline in clinical laboratory values will be descriptively

Protocol 31-14-204

summarized by visit for the Open-label Safety Sample and also by treatment group for the Randomized Safety Sample.

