9.5 Electrocardiogram Data

All ECG analyses are made using observed data. Baseline is defined as average of ECG measurements at baseline visit as specified in [Section 5.2](#). Last visit for each phase is defined as average of ECG measurements at last visit as specified in [Section 5.2](#). Missing ECG data will not be imputed. For the calculation of QT correction by heart rate, QTc is missing only if all three consecutive beats are unreadable. If there is at least 1 beat available in the lead, the data are included in the analysis. For each ECG, QT and RR

intervals from three consecutive complexes (representing three consecutive heart beats) are measured manually. The QT correction is performed on beat-to-beat basis. The mean of ratios (beat-to-beat) is calculated by $(QT_{c1} + QT_{c2} + QT_{c3})/3$ using each QT-RR pair: (QT1, RR1), (QT2, RR2) and (QT3, RR3). The corrected QT intervals for QT_{cB}, QT_{cF}, and QT_{cN} are defined as follows:

- QT_{cB} is the length of the QT interval corrected for heart rate by Bazett's formula: $QT_{cB} = QT / (RR)^{1/2}$.
- QT_{cF} is the length of the QT interval corrected for heart rate by Fredericia's formula: $QT_{cF} = QT / (RR)^{1/3}$.
- QT_{cN} is the length of the QT interval corrected for heart rate by the FDA Neuropharm Division formula: $QT_{cN} = QT/(RR)^{0.37}$.

Potentially clinically relevant ECG abnormalities will be listed by subject. Criteria for identifying ECG measurements of the potentially clinically relevance are provided in [Appendix 3](#). The incidences of abnormal ECGs of potential clinical relevance based on the observation at the scheduled and the unscheduled post-baseline visits will be tabulated the safety samples. Descriptive statistics of change from baseline in ECG intervals of PR, QRS, RR, QT, QT_{cB}, QT_{cF}, and QT_{cN} will be presented at each scheduled trial week and last visit for the safety samples.

In summarizing the incidence of abnormalities, a patient must have had an evaluation that meets abnormality criteria by the end of trial phase. Incidence rate is calculated as the number of patients having at least 1 abnormality within the corresponding study phase divided by the number of patients who are both exposed to study medication and have an on-treatment evaluation within the same study phase.

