Appendix 1 Criteria for Identifying Laboratory Values of Potential Clinical Relevance

Laboratory Tests	Criteria
Chemistry^a	
AST (SGOT)	≥ 3 x ULN
ALT (SGPT)	≥ 3 x ULN
Alkaline phosphatase	≥ 3 x ULN
LDH	≥ 3 x ULN
BUN	≥ 30 mg/dL
Creatinine	≥ 2.0 mg/dL
Uric Acid	
Male	≥ 10.5 mg/dL
Female	≥ 8.5 mg/dL
Bilirubin (total)	≥ 2.0 mg/dL
CPK	≥ 3 x ULN
Prolactin	> ULN
Hematology^a	
Hematocrit	≤ 30 % and decrease of ≥ 3 percentage points from baseline
Hemoglobin	
Male	≤ 11.5 g/dL
Female	≤ 9.5 g/dL
White blood count	≤ 2,800 mm ³ or ≥ 16,000 mm ³
Eosinophils	≥ 10%
Neutrophils	≤ 1.5 THOUS/μL
Platelet count	≤ 75,000/ mm ³
Urinalysis^a	
Protein	Increase of ≥ 2 units
Glucose	Increase of ≥ 2 units
Casts	Increase of ≥ 2 units
Additional Criteria	
Chloride	≤ 90 mEq/L or ≥ 118 mEq/L
Hb1Ac	≥ 7%
Potassium	≤ 3.0 mEq/L or ≥ 5.5 mEq/L
Sodium	≤ 120 mEq/L or ≥ 160 mEq/L
Phosphorous, inorganic	≤ 1.0 mg/dL
Magnesium, serum	≤ 0.7 mEq/L or ≥ 5.0 mEq/L
Calcium	≤ 8.2 mg/dL or ≥ 12 mg/dL
Glucose, Fasting, serum	≥ 115 mg/dL
Total Cholesterol, Fasting	≥ 240 mg/dL
LDL Cholesterol, Fasting	≥ 160 mg/dL
HDL Cholesterol, Fasting	≤ 30 mg/dL
Triglycerides, Fasting	
Male	≥ 160 mg/dL
Female	≥ 120 mg/dL

^a As defined in "Supplementary Suggestions for Preparing an Integrated Summary of Safety Information in an Original NDA Submission and for Organizing Information in Periodic Safety Updates," FDA Division of Neuropharmacological Drug Products draft (2/27/87).

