Appendix 2 Criteria for Identifying Vital Signs of Potential Clinical Relevance

Variable	Criterion Value^a	Change Relative to Baseline^a
Heart Rate ^b	> 120 bpm < 50 bpm	≥ 15 bpm increase ≥ 15 bpm decrease
Systolic Blood Pressure ^b	> 180 mmHg < 90 mmHg	≥ 20 mmHg increase ≥ 20 mmHg decrease
Diastolic Blood Pressure ^b	> 105 mmHg < 50 mmHg	≥ 15 mmHg increase ≥ 15 mmHg decrease
Weight	-	≥ 7% increase ≥ 7% decrease

^a In order to be identified as potentially clinically relevant, an on-treatment value must meet the “Criterion Value” and also represent a change from the subject’s baseline value of at least the magnitude shown in the “Change Relative to Baseline” column.

^b As defined in “Supplementary Suggestions for Preparing an Integrated Summary of Safety Information in an Original NDA Submission and for Organizing Information in Periodic Safety Updates,” FDA Division of Neuropharmacological Drug Products draft (2/27/87).

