- CT-16.1.4 Laboratory Test Results for Other Clinical Laboratory Tests - Mean Change from Baseline (Open-Label Safety Sample)
- CT-16.2 Incidence of Laboratory Values of Potential Clinical Relevance (Open-Label Safety Sample)
- CT-17.1.1 Vital Sign Parameters - Mean Change from Baseline (Open-Label Safety Sample)
- CT-17.1.2 Mean Change from Baseline in Weight, Height, BMI and Waist Circumference (Open-Label Safety Sample)
- CT-17.2 Incidence of Vital Signs of Potential Clinical Relevance (Open-Label Safety Sample)
- CT-18.1 ECG Parameters - Mean Change from Baseline (Open-Label Safety Sample)
- CT-18.2 Incidence of ECG Measurements of Potential Clinical Relevance (Open-Label Safety Sample)

- DREAS-1 Discontinued Subjects and Reasons for Discontinuation
- DREAS-2 Adverse Events for Subjects Who Discontinued from Trial due to Withdrew Consent
- PDEV-1 Protocol Deviations by Phase and Type of Deviation (Enrolled Sample)
- PDEV-2 Protocol Deviations by Phase, Country, Center and Type of Deviation (Enrolled Sample)
- PDEV-3 All Protocol Deviations by Subject
- PDEV-4 Protocol Deviations Criteria
- DEMOG-1 Demographic Characteristics
- SMED-1.1 Summary of Trial Medication Compliance in Double-Blind Randomized Withdrawal Phase (Randomized Sample)
- SMED-1.2 Trial Medication Compliance in Double-Blind Randomized Withdrawal Phase (Randomized Sample)
- SMED-2.1 Summary of Trial Medication Compliance in Open-Label Stabilization Phase (Enrolled Sample)
- SMED-2.2 Trial Medication Compliance in Open-Label Stabilization Phase (Enrolled Sample)

Protocol 31-14-204

EFF-1 Relapse Data

EFF-2.1 Yale Global Tic Severity Scale - Total Tic Score (YGTSS - TTS) and Total Yale Global Tic Severity Scale Score

EFF-2.2 Clinical Global Impressions Scale for Tourette's Syndrome (CGI-TS) Severity and Improvement Scores

AE-1.1 Adverse Events in Open-Label Stabilization Phase (Enrolled Sample)

AE-1.2 Adverse Events in Double-Blind Randomized Withdrawal Phase (Randomized Sample)

AE-1.3 Adverse Events in Follow-up Period (Enrolled Sample)

LAB-1 Laboratory Test Results: Serum Chemistry

LAB-2 Laboratory Test Results: Hematology

LAB-3 Laboratory Test Results: Urinalysis

LAB-4 Laboratory Test Results: Other Laboratory Tests

LAB-5 Laboratory Test Results: Urine Drug Screen

LAB-6 Laboratory Test Results: Urine Pregnancy Test (Enrolled Sample)

Proposed Patient Data Listings

PDATA-1 Consents and Eligibility

PDATA-2 Randomization List

PDATA-3.1 Subject Disposition

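### For 27 of the 31 laboratory criteria, the SAP's incidence tables do not separate values already flagged at the phase baseline from new ones

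*SAP*

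**What the plan says.** SAP 9.3 builds the laboratory incidence tables (CT-16.2 for the open-label phase, CT-10.2 for the double-blind phase) from the criteria in Appendix 1: "The incidences of potentially clinically relevant laboratory tests abnormalities based on the observation from the scheduled and the unscheduled post-baseline visits will be tabulated". It sets no condition on the baseline value and names no denominator. The SAP defines an incidence rate only in its ECG section, 9.5, where the denominator is the "number of patients who are both exposed to study medication and have an on-treatment evaluation within the same study phase". That definition removes nobody for a value already abnormal at baseline. Protocol 7.6.2 adds no condition either: "The incidence of potentially clinically relevant values from clinical laboratory tests will be provided for the open-label stabilization phase and by treatment group" in the withdrawal phase.

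Most Appendix 1 criteria are absolute cut-offs, such as "≤ 1.5 THOUS/μL" for neutrophils. Hematocrit also requires a fall from baseline, and urine protein, glucose and casts are defined as increases. Appendices 2 and 3 work differently. For vital signs and ECG, footnote a requires a value to meet its cut-off "and also represent a change from the subject", the comparison being with that subject's baseline value.

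At entry, Protocol 3.4.3 (criterion 20) excludes "Hemoglobin ≤ 9 g/dL" and neutrophils at or below 1000/mm³. It sets no numeric limit for prolactin, fasting glucose, lipids or eosinophils. A note to that criterion also excludes other abnormal values that the investigator judges medically significant.

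**The concern.** For an absolute cut-off, a child who met it before the phase began and meets it again afterwards is counted exactly like a child in whom it arose during the phase. A boy with hemoglobin of 11.2 g/dL, or a child with neutrophils of 1.2 thousand/µL, passes the numeric entry limits. If the value does not move, he appears in CT-16.2 and, if randomized, again in CT-10.2 under whichever arm he is given.

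The double-blind table has a second source of such values. Under SAP 5.2 its baseline is the last open-label visit, which comes after 14 to 20 weeks of aripiprazole. A flag that arose on open-label drug and persists is counted as double-blind incidence, including under placebo.

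These tables serve the secondary (safety) objective. CT-16.2 has no control arm, so its reader cannot tell background from new cases. In CT-10.2 the two are mixed within each arm. The SAP takes account of the starting value elsewhere: in Appendices 2 and 3, in the liver listing in 9.3, and in the treatment of events that continue from a phase baseline in the TEAE definition in 9.2.

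**Working it through.** The plan states no figure on this point, so there is none to reproduce. The check is a count, a comparison of limits, and an illustration.

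**1. Criteria without a baseline element (SAP Appendix 1).** Chemistry has 10 tests, hematology 6, urinalysis 3 and the additional criteria 12: 10 + 6 + 3 + 12 = 31. Four carry a change condition (hematocrit; urine protein, glucose and casts). That leaves 31 − 4 = 27, or 87%, as absolute cut-offs.

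**2. Can an eligible child already meet one of the 27?** Protocol 3.4.3, criterion 20, against SAP Appendix 1:

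| Test | Excluded at entry | Flagged | Numeric room to enter flagged |
|---|---|---|---|
| Hemoglobin, male | ≤ 9 g/dL | ≤ 11.5 g/dL | above 9, up to 11.5 |
| Hemoglobin, female | ≤ 9 g/dL | ≤ 9.5 g/dL | above 9, up to 9.5 |
| Neutrophils | ≤ 1000/mm³ | ≤ 1500/mm³ | above 1000, up to 1500 |
| AST, ALT | > 3 × ULN | ≥ 3 × ULN | exactly 3 × ULN |
| Creatinine | ≥ 2 mg/dL | ≥ 2.0 mg/dL | none |
| Platelets | ≤ 75,000/mm³ | ≤ 75,000/mm³ | none |
| Other 21 tests | no numeric limit | various | investigator judgement only |

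By test: 2 with a numeric gap, 2 closed except at the boundary, 2 closed, 21 with no numeric limit; 2 + 2 + 2 + 21 = 27.

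**3. The second baseline.** These limits are entry criteria. Samples are drawn at the randomization visit (Protocol 3.7.1.6.1), but no numeric laboratory limit is restated there. Any of the 27 flags can therefore be present at the double-blind baseline.

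**4. Size (illustration; every rate is assumed).** Let p be the share flagged at the phase baseline, all of whom meet the flag again, and e the new-case rate among the rest. The tabulated incidence is p + (1 − p)e. Take e = 2% in one arm and 8% in the other, so the new-case ratio is 4 and the difference 6.0 points.

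| p | Arm with e = 2% | Arm with e = 8% | Ratio | Difference |
|---|---|---|---|---|
| 5% | 0.05 + 0.95 × 0.02 = 6.9% | 0.05 + 0.95 × 0.08 = 12.6% | 1.8 | 5.7 points |
| 10% | 0.10 + 0.90 × 0.02 = 11.8% | 0.10 + 0.90 × 0.08 = 17.2% | 1.5 | 5.4 points |
| 20% | 0.20 + 0.80 × 0.02 = 21.6% | 0.20 + 0.80 × 0.08 = 26.4% | 1.2 | 4.8 points |

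The difference shrinks only by the factor (1 − p). At the planned 38 per arm and p = 10%, the table would show 38 × 0.118 = 4.5 and 38 × 0.172 = 6.5 subjects on average, of whom 38 × 0.10 = 3.8 in each arm were flagged at the start.

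**5. If persistence differs by arm.** Let s be the share of pre-existing flags met again. The tabulated incidence is then ps + (1 − p)e, and the difference between arms gains a term p(s₁ − s₂). A flag caused by the drug could resolve on placebo and persist on full dose, so the background need not be equal across arms.

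**The case against.** The strongest case on the other side has five parts.

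- **Entry safeguards.** The note to criterion 20 points investigators to Protocol Appendix 2, whose cut-offs are those of SAP Appendix 1. Protocol 3.7.3.2 bars enrollment after a clinically significant screening result unless the medical monitor permits it. These safeguards reduce the number affected, but they are discretionary and apply at entry only. Prolactin results are also blinded. What stands is that the number cannot be derived from the documents.
- **Neighbouring outputs.** SAP 9.3 also gives changes from baseline by week, and values are listed by subject. Under Protocol 5.1 medically relevant values become adverse events. This softens the problem. Mean changes do not identify new cases, however, listings leave the reader to reconstruct them, and none of the laboratory summary tables in Appendix 4 is a shift table.
- **Title and source.** The tables are titled as values of potential clinical relevance, not as treatment-emergent, and most of the criteria are attributed to a regulator's draft. That is fair, but the question is who is counted as incident, not where the cut-offs lie.
- **Scale.** On the difference scale the distortion is small, as step 4 shows. This stands.
- **The simple remedy.** Limiting CT-10.2 to subjects free of the flag at phase baseline would drop every abnormality that arose on open-label drug, and with it persistence against resolution by arm, a contrast that a randomized withdrawal can show. This stands and shapes the fix.

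A reader might infer that the laboratory tables have no baseline condition at all. Four tests have one. A reader might also infer that every pre-existing abnormality is counted automatically. It is counted only if the cut-off is met again after baseline.

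**Conclusion.** The concern holds for the 27 absolute cut-offs. As written, SAP 9.3 reports pre-existing values that recur after baseline as incidence within the phase: in CT-16.2, and in every arm of CT-10.2.

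Under the assumptions in step 4, with 10% pre-existing and all persisting, new-case rates of 2% and 8% read as 11.8% and 17.2%. The ratio drops from 4 to 1.5, and the difference from 6.0 to 5.4 points. The real size is unknown, because the documents give neither the share flagged at baseline nor its persistence.

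It is tempting to say that the rule adds the same background to every arm and so hides real differences. The documents do not support that: persistence may differ by arm, and on the difference scale the loss is modest even when it does not.

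The trial ended early, efficacy reporting is descriptive, and no test or decision rests on these two tables. This is a minor improvement to descriptive safety reporting.

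**What to change.** In SAP 9.3, for the 27 absolute-cut-off tests, present CT-16.2 and CT-10.2 by status at that phase's baseline (SAP 5.2):

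- the number and percentage with a new occurrence among subjects who did not meet the criterion at the phase baseline, using those subjects as the denominator and stating so;
- the number already meeting the criterion at the phase baseline;
- of these, the number still meeting it after baseline.

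Give all three by arm in CT-10.2. Say where subjects without a baseline value are shown. Leave every cut-off as it is, and keep the listings CT-10.3.1 and CT-10.3.2 unrestricted so that worsening from an abnormal start stays visible.

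The cost is programming only, since samples are already scheduled at screening and at randomization. The price is a few extra rows per test and somewhat smaller denominators for the new-occurrence rows.
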